2.7.2 Outcome measures

Outcome measures will be evaluated to ensure they are appropriate for use in a large, multi-centre trial and balance respondent burden, cost of data collection and value of the data appropriately. Implications for application of these outcome measures will be assessed through consultation with patients via the qualitative study and research clinicians via informal feedback.

Primary and secondary outcome measurements will be taken at baseline and six months. This will allow time for the interventions to be completed and will allow us to assess the feasibility of data collection and adherence to the exercise interventions.

2.7.2.1 Primary outcome measure

The primary outcome measure for the pilot RCT will be Cobb angles as measured by X-ray at 6 months after randomisation. We anticipate that the primary outcome measures for a main RCT study will be the progression/stabilisation of curvature quantified by the Cobb angle. Traditionally the measurement of Cobb angle required repeat X-ray but many centres have invested in topographical measurement equipment (e.g. ISIS-2 measurement system) that allows for assessment of Cobb angle and rib hump without exposure to X-ray. We will explore whether it will be feasible/cost-effective to use the ISIS-2 measurement system in all centres in the main trial (as it might be the case that equipment has to be purchased for some sites). Although the measurement of outcome is not essential to the assessment of feasibility, we feel it is prudent to capture outcomes as it is likely that the pilot could contribute data to a future definitive trial (and hence reduce the cost). In our proposed time table we will probably not have 6 month outcome for all participants. This data is not needed for the assessment of feasibility. However, we will continue to collect the follow up data after the end of the funded study period, so that the data are available for later publication and/or inclusion in a future definitive trial if appropriate. The data will be made available to the funders.

2.7.2.2 Secondary outcomes

We will also pilot a range of secondary outcomes. There are a range of quality of life measures available for AIS - an expert consensus meeting suggested that aesthetics, quality of life, disability, back pain and psychological well-being were the most important outcomes for conservative treatment of AIS (Negrini et al. 2006). Based on this we will collect the following data:

 Disease specific functional measure: Scoliosis Research Society 22 Questionnaire (Asher et al. 2003)

- Participant perceived spinal deformity: Spinal Appearance Questionnaire (Sanders et al. 2007)
- Generic functional measure: Paediatric Outcomes Data Collection Instrument (Lerman, Sullivan and Haynes 2002)
- Exercise tolerance and respiratory function
- Health related quality of life measures: EQ-5D, Health Utilities Index and SF-12
- Resource use for economic analysis
- Brace wearing status
- Progression to surgery

2.8 Sample size

We will not be able to estimate the effect size for exercise in the pilot trial with any reasonable degree of certainty, but we have sized the pilot trial so that we can estimate the baseline variance in the outcome measures which is one of the most important drivers of any sample size estimate. A minimum of 30 participants are needed to estimate the variance of parameters underlying the sample size estimate (Lancaster, Dodd and Williamson 2004). We have chosen a target of 50 as this allows for better estimation of recruitment rates at each of the three centres. We plan to synthesise data from the systematic review, clinical opinion and the pilot data to derive a target effect size for the main trial.

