2.4 Eligibility for pilot RCT

2.4.1 Inclusion criteria

- 10-16 years olds with Adolescent Idiopathic Scoliosis (AIS).
- Mild to moderate AIS, defined by a Cobb angle of between 10 50° (measured radiographically).

2.4.2 Exclusion criteria:

- Individuals who have had previous surgery or are on a waiting list for spinal surgery within the next 6 months.
- Individuals with non-idiopathic scoliosis, for example congenital malformations, syringomyelia, neurofibromatosis, spina bifida, polio and cerebral palsy.

[figure not shown]
Other treatments including bracing and previous physiotherapy are not exclusion criteria.

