2.7 Outcome Measures

2.7.1 Criteria for progression to a randomised controlled trial

The primary outcome of this feasibility trial is to assess if the criteria for progression to a full RCT has been achieved. The progression criteria will be:

1. To demonstrate that the assumptions underlying the sample size, in particular the rates of progression are as anticipated in three centres, that variances are within our estimated range, and that we can achieve or better the recruitment target in these three centres.

We estimate the definitive trial will include between 300-400 participants. This would allow detection of a standardised difference of 0.3, equating to a clinically important 6 degree difference between groups in the Cobb angle (Negrini et al. 2010) (SD of 15 degrees using 80% power, alpha <.05, loss to follow-up of 30%), and also a relative risk reduction of 1.4 in the numbers proceeding to surgery, assuming that 20% of the control group progress to surgery.

2. That we have sufficient numbers of centres, with sufficient numbers of participants in order to finalise the recruitment strategy for a main trial.

Thirty-five NHS Trusts managing AIS in the UK have been identified that could potentially recruit participants in the main trial. There is a wide range of permutations of time, rate of recruitment and number of centres recruiting that could achieve the anticipated sample size but the optimal strategy needs to be finalised. We will also be able to confirm whether patients and their families are willing to accept randomisation as opposed to sourcing exercises themselves, and whether our estimates of the numbers potentially eligible, meeting the various inclusion and exclusion criteria, and finally being randomised are accurate.

3. To have developed an intervention which, based on theoretical models, has sufficient therapeutic dose to limit or reverse progression of curvature and has maximal chance of engaging adherence in adolescents. We must demonstrate that we can deliver a theoretically sufficient dose within current and reasonable levels of NHS resourcing, and that greater than 60% of adolescents will have attended all

supervised sessions and provide evidence that they are undertaking exercises at home.

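### The pilot is sized on baseline variance, which the 10 to 50 degree entry range restricts, while the progression check needs the spread of follow-up Cobb angle or its change, and the 6-month data that give it are set aside

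*Protocol*

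**What the plan says.** All references are to the protocol.

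- **Section 2.8 (sample size).** The stated basis for the pilot's size is that "we have sized the pilot trial so that we can estimate the baseline variance in the outcome measures". It adds that "A minimum of 30 participants are needed to estimate the variance of parameters underlying the sample size estimate", and explains the larger number by recruitment: "We have chosen a target of 50 as this allows for better estimation of recruitment rates at each of the three centres".
- **Section 2.7.1 (progression criteria).** Criterion 1 requires that progression rates are as anticipated and "that variances are within our estimated range". The only spread given is a single SD of 15 degrees. It stands beside a standardised difference of 0.3, a difference of 6 degrees, 80% power, alpha 0.05 and 30% loss. From these the section concludes: "We estimate the definitive trial will include between 300-400 participants".
- **Section 2.7.2.1 (primary outcome measure).** The pilot's primary outcome measure is the X-ray Cobb angle at 6 months. For the main trial: "We anticipate that the primary outcome measures for a main RCT study will be the progression/stabilisation of curvature quantified by the Cobb angle". The same section expects 6-month outcomes to be incomplete within the timetable and says that feasibility can be judged without them.
- **Section 2.4.1 (inclusion criteria).** Entry is limited to a radiographic Cobb angle from 10 to 50 degrees.
- **Section 6.1.** The parameters and variances needed for the sample size will be reported, without saying which.

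**The concern.** A trial comparing curve progression is sized on the spread of the follow-up angle, of its change from baseline, or of what remains after adjustment for baseline. The baseline SD alone supplies none of these, because the correlation between baseline and follow-up is missing.

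For the Cobb angle the baseline SD is also limited by the entry rule, whereas the follow-up SD is not. Comparing a restricted baseline SD with an assumed 15 is thus a lopsided check.

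At stake is whether the definitive trial is sized correctly in a condition that section 1.3 describes as fairly rare. An SD that is too low gives an underpowered trial. An SD that ignores a strong baseline correlation recruits more adolescents than needed.

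**Working it through.** **Inputs.** Difference 6 degrees, SD 15, 80% power, alpha 0.05, 30% loss (section 2.7.1); entry range 10 to 50 degrees (2.4.1); pilot of 50 and minimum of 30 (2.8). Assumed here, because not stated: two-sided test, 1:1 allocation, and all correlations r.

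**Formula.** Per arm, n = 2(1.960 + 0.842)² × SD² / 6², which is 0.436 × SD². Double this and divide by 0.70 for loss. An exact t-test calculation adds about one participant per arm.

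**1. The plan's own figure.**
- 6/15 = 0.40: 99 per arm, 198 in total, 198/0.70 = 283 randomised (286 by t-test).
- Standardised difference 0.30, which for 6 degrees means SD 6/0.30 = 20: 175 per arm, 350 in total, 350/0.70 = 500 randomised.

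Neither full set of inputs falls in the 300 to 400 of section 2.7.1. The second matches the top of the 400 to 500 in section 1.3. It is therefore unclear whether the SD to be checked is 15 or 20.

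**2. What a baseline SD can show.** The entry range is 40 degrees wide.
- Truncated normal distributions (centre 20 to 40, underlying SD 10 to 25): SD 7.9 to 11.1.
- Uniform: 40/√12 = 11.5.
- Largest for any single-peaked distribution: 40/3 = 13.3.
- Absolute maximum, half at each limit: 40/2 = 20.

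In 200,000 simulated uniform samples of 50, none had an SD of 15 or more; the largest was 14.7.

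**3. Size of the error, in both directions** (6 degrees, 80% power, 30% loss).

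| SD used | Per arm | Randomised |
|---|---|---|
| 11.5 (uniform baseline) | 59 | 118/0.70 = 169 |
| 13.3 | 78 | 156/0.70 = 223 |
| 15 | 99 | 198/0.70 = 283 |
| 15, baseline-adjusted, r = 0.8: 15 × √(1 − 0.64) = 9.0 | 36 | 72/0.70 = 103 (106 by t-test) |

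- Too small: with 59 per arm and a true SD of 15, 6/(15 × √(2/59)) = 2.17. Power is the normal probability below 2.17 − 1.96 = 0.21, about 58%.
- Too large: if SD 15 holds at both visits and r = 0.8, the SD of change is 15 × √(2 × 0.2) = 9.5. That needs 115 randomised if change is analysed, or 103 with adjustment, against 283.

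**4. What the 6-month data would give.** With 30% loss, 35 of 50 remain.
- An observed SD of 15 has a 95% CI of 15 × 0.809 to 15 × 1.310, that is 12.1 to 19.7. With all 50 it is 12.5 to 18.7.
- For r = 0.8 on 35 pairs, Fisher's z is 1.099 ± 1.96/√32, giving about 0.64 to 0.89. At SD 15, those limits unrounded (0.636 and 0.895) correspond to 169 down to 58 randomised.

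**5. Timing.** Section 7.4 has a 6-month development phase, 12 months of recruitment, and analysis from month 20. If recruitment runs evenly over months 6 to 18 (an assumption), those randomised by month 14 have reached 6 months when analysis begins: 50 × 8/12 = 33. After 30% loss about 23 remain, below the minimum of 30 in section 2.8. Later data could be added before month 24, but nothing requires it.

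**The case against.** The strongest reply is that section 2.8 says what the pilot was sized on, not which variances it will report. Section 6.1 promises the variances needed for the final calculation. Six-month Cobb angle is scheduled in Table 1 and has no entry limit. Section 7.4 aims to follow everyone up within the study, and 35 of 50 would exceed the minimum of 30.

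This stands as far as it goes, so a reader should not infer that the pilot cannot test the SD of 15. But section 6.1 does not say which variances, and section 2.7.2.1 takes the 6-month data out of the feasibility judgement. The one variance the plan names is the baseline one.

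Three further objections stand:

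- It is tempting to conclude that this part of criterion 1 cannot fail. The criterion speaks of a range, not an upper limit. A baseline SD of 8 to 11.5 could fall below a range around 15, and would be real evidence that 15 is too large for the unadjusted angle. Without numeric limits the check is undefined rather than impossible to fail.
- The restriction concerns the Cobb angle only. Section 2.8 speaks of several outcome measures, and the questionnaires are not limited by the entry angle.
- Section 2.7.1 sizes on the SD of the angle itself, so baseline spread is a legitimate partial input.

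**Conclusion.** The point holds in a limited form. The plan names the less suitable variance as the basis for the pilot's size. It sets aside the paired 6-month data that would give the right one, and makes progression depend on variances without saying which or within what limits. Sections 2.7.1, 2.7.2.1 and 2.8 do not fit together. A baseline check of the Cobb angle is one-sided rather than empty: it can point to 15 being too large, and would show it too small only with a clearly two-peaked sample.

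The consequence runs from 169 randomised with about 58% power, if 11.5 is used and 15 is true, to 283 where about 103 might do. The lower figure rests on an assumed r of 0.8, which the protocol does not give. A reader might infer that the definitive trial would most likely come out too large. The documents do not support a direction, since it depends on the follow-up SD and on r. Nor do they support requiring the future trial to be sized on a baseline-adjusted residual SD: its protocol is still to be written, and r over 6 months may be higher than over a longer follow-up.

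**What to change.** 1. Reconcile 0.3, 6 degrees and SD 15 in section 2.7.1, and the totals in sections 1.3 and 2.7.1, so that it is clear which SD is to be checked.
2. In section 2.8, criterion 1 and section 6.1, name the variance parameters to be reported, each with a 95% CI: within-arm SD of the 6-month Cobb angle, SD of change, and baseline-to-6-month correlation.
3. Apply criterion 1 to the follow-up or change SD, with numeric limits stated in advance. Keep the baseline SD as a descriptive figure.
4. Replace the statement in section 2.7.2.1 so that the 6-month data available at the progression decision are used, and report how many participants contribute.
5. Report the baseline-adjusted residual SD as one input to the definitive sample size, not a mandatory basis, with the caution about longer follow-up.

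The cost is wording and a few lines of analysis, because both measurements are already scheduled. The drawback is that 6-month data may be incomplete at the decision, so the intervals will be wide and the numeric range should allow for that.

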2.9 Recruitment and randomisation

2.9.1 Identifying potential participants

We plan to run the randomised pilot trial in 3 of the 35 NHS trusts specialising in scoliosis management. Participants will be recruited directly from spinal deformity or scolioisis clinics at the three centres. Patients with AIS will be approached to participate in the feasibility study by clinicians who will be supported by a physiotherapy research fellow and/or CLRN research nurses. We have reviewed attendance rates at each of the feasibility sites and, for the types of participants we seek, expect referral of around 4 eligible participants per month per site. Assuming 40% agree to participate, we will recruit 5 participants per month during the feasibility stage, and require an estimated 10-12 months to achieve the target of 50 participants.

2.9.2 Method of randomisation

Randomisation will be on an individual basis using the WCTU telephone randomisation service. Randomisation will be stratified by centre to control for any local differences and in case mix between sites. For the main study we anticipate stratifying randomisation by bracing regime at study entry and we will evaluate this in the feasibility stage.

2.10 Post-randomisation withdrawals and exclusions

Participants may withdraw from the trial intervention, and/or the whole trial at any time without prejudice. If a participant withdraws from the trial intervention, participants will be followed-up wherever possible and data collected as per protocol until the end of the trial. The only exception to this is where the participant also explicitly withdraws consent for follow-up.

Participants may also be withdrawn from the trial at the discretion of the Chief Investigator, the lead local investigator and/or Independent Monitoring Committee due to safety concerns.

2.11 Blinding of treatment allocation

It will be impossible to blind the therapists involved in delivering the interventions and the participants receiving them. However we will structure the outcome assessment so that outcome assessors are blinded. We will test the integrity of the blinding by asking assessors to guess which allocation participants had at the 6 month follow up point.

2.12 Compliance/contamination

During the pilot RCT, the treating therapists will record the number of physiotherapy sessions attended by each participant and the content of the physiotherapy session on a treatment log. Participants will also complete an online-exercise diary so that compliance with the home exercise programme can be monitored.

We will periodically observe the consent process and baseline and follow-up assessments. Quality control visits will also be carried out to observe physiotherapy sessions. Quality assurance checks will be undertaken by the WCTU to ensure the integrity of randomisation, study entry procedures and data collection.

3 Methods and Assessments

3.1 Schedule of delivery of intervention and data collection

Table 1 Pilot RCT events

Event/information collected	Usual clinic appointment	Baseline assessment & randomisation	Exercise intervention delivered over 6 months (6-9 sessions)	Control intervention 1-2 sessions	Follow up assessment (6 months post randomisation)
Initial screening of participants	\checkmark				
expressing interest:					
Inclusion/exclusion criteria		,			
Demographics and past medical history		√			
Cobb angle:	\checkmark	\checkmark			$\sqrt{}$
X-ray and ISIS-2 measurements					
Disease specific functional		\checkmark			√
measure: Scoliosis Research					
Society 22 Questionnaire					
Generic functional measure:					√
Paediatric Outcome Data					
Collection Instrument		,			,
Participant perceived spinal		√			√
deformity: Spinal Appearance					
Questionnaire		/			
Quality of life: EQ5D, Health Utilities Index, SF-12		√			√
Brace wearing status					$\sqrt{}$
Intervention delivered			√	√	
Treatment log completed by			√	√	
physiotherapist					
Online exercise diary completed					
by participant					
Recording of any progression to					√
surgery					

4 Adverse Event Management

4.1 Definitions

4.1.1 Adverse Events (AE)

An adverse event is defined as any untoward medical occurrence in a subject which does not necessarily have a causal relationship with this treatment.

4.1.2 Serious Adverse Events (SAEs)

An SAE is an AE that fulfils one or more of the following criteria:

- Results in death
- Is immediately life-threatening
- Requires hospitalisation or prolongation of existing hospitalisation
- Results in persistent or significant disability or incapacity
- Is a congenital abnormality or birth defect
- Is an important medical condition.

4.2 Reporting SAEs during the pilot RCT

In addition to those described above. We will define the following as a serious adverse event:

A significant increase or onset of pain or other symptoms (e.g. neurological symptoms) within 48 hours of attending a physiotherapy session or taking part in an exercise session causing the participant to reduce their normal activities (e.g. absence from school, cutting down on sport) for greater than 3 days.

Due to the nature of AIS and exercise therapy, it is expected that the following may occur during the pilot RCT and, therefore, will not be reported to the MREC. They will be recorded as an AE:

The participant needs surgery due to curve progression.

The participant needs bracing due to curve progression.

Mild muscle soreness normally associated with exercise (lasting up to 48 hours).

All adverse events will be recorded in the Case Report Form (CRF) for participants by local clinical and research staff at assessment for routine return to the research office. Any AEs fitting the criteria for 'serious' as defined above will be recorded on the SAE report form provided and faxed to WCTU ([contact]) within 24 hours of the investigator becoming aware of the event. Physiotherapists who deliver the interventions

will be trained in the reporting of AE and SAEs. All SAEs will be recorded in the trial database and reported to the Independent Monitoring Committee.

The study manager will liaise with the clinician to compile all the necessary information. The Trial Co-ordinating Centre is responsible for reporting adverse events to the sponsor and ethics committee within required timelines. The causality of SAEs (i.e. relationship to trial treatment) will be assessed by the Principal Investigator at the site involved and the Chief Investigator and this will be recorded on the SAE form. SAE's which are deemed to be both unexpected and related to the intervention will be reported to the main REC within 15 days of receipt.

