1.1 Epidemiology and burden of condition

Adolescent Idiopathic Scoliosis (AIS) is often referred to as a structural lateral curvature of the spine, although, it is actually a 3 dimensional spinal deformity that results in lateral deviation, rotation and flexion/extension of the vertebrae. It is of unknown cause that occurs at or near the onset of puberty(Lonstein 2006). AIS is commonly diagnosed using the Cobb Angle and to meet the definition the lateral curvature must have a Cobb angle of greater than 10 degrees. A Cobb angle is measured using standing postero-anterior radiographs of the full spine and assesses the lateral curvature of the spine. To do this the most tilted vertebrae above and below the apex of the curve is identified. The angle between intersecting lines drawn perpendicular to the top of the top vertebrae and the bottom of the bottom vertebrae is the Cobb angle (See Figure 1).

[figure not shown]

Figure 1 Measurement of Cobb Angle

The prevalence of AIS in children aged 10-16 years is 1-3% (Parent, Newton and Wenger 2005, Kesling and Reinker 1997), implying 50,000 - 150,000 sufferers in the UK (Office 2009). The effects of AIS include pain, cosmetic concerns, functional limitations, cardiorespiratory problems and possible further curve progression in adulthood (Weinstein et al.

2003). About 10% of AIS cases require surgical or active conservative management (UK 2010). Current UK management includes monitoring, bracing for some and, for the most progressive and serious cases, surgery. Surgery is generally only undertaken when spinal curvature reaches a Cobb angle >45-50 degrees (Weinstein et al. 2008). Surgery is a very extensive procedure, with exposure of large segments of the spine and substantial fixation which, whilst reducing curve progression, also permanently limits mobility in the affected part of the spine. Surgery also comes with a risk of complications estimated to occur in approximately 6% of patients undergoing spinal fusion for scoliosis and include pulmonary complications, wound infection and neurological damage (Coe et al. 2006).

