7.7 Independent monitoring committee

As this is a feasibility study a Trial Steering Committee and Data Monitoring and Ethics Committee will not be appointed. Instead, an Independent Monitoring Committee will be appointed to primarily review serious adverse events.

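### Sections 4.1.2 and 4.2 conflict on whether a surgical admission for curve progression is an SAE, and the session-linked SAE criterion observes the two arms unequally

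*Protocol*

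**What the plan says.** Protocol section 4.1.2 gives the general criteria for a serious adverse event, among them "Requires hospitalisation or prolongation of existing hospitalisation". Section 1.1 describes the operation: "Surgery is a very extensive procedure, with exposure of large segments of the spine and substantial fixation".

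Section 4.2 adds three things.

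- **Expected events.** A short list of events expected from the condition or from exercise "will not be reported to the MREC. They will be recorded as an AE". The first item is "The participant needs surgery due to curve progression". New bracing for progression and mild muscle soreness follow.
- **Serious events.** "Any AEs fitting the criteria for 'serious' as defined above will be recorded on the SAE report form provided", and this is to reach the trials unit within 24 hours. "All SAEs will be recorded in the trial database and reported to the Independent Monitoring Committee". Only SAEs that are both unexpected and related to the intervention go to the main ethics committee, within 15 days.
- **An additional SAE criterion.** A significant onset or increase of pain or other symptoms that restricts normal activities for more than 3 days also counts as serious, if it arises "within 48 hours of attending a physiotherapy session or taking part in an exercise session".

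Section 7.7 states that there will be no steering committee or data monitoring committee; instead "an Independent Monitoring Committee will be appointed to primarily review serious adverse events". Under section 4.3 that committee's recommendation can stop the trial.

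**The concern.** An event can be expected and still be serious. Expectedness bears on who must be told quickly; seriousness bears on what the event is. By recording surgery for progression as an AE because it is expected, section 4.2 merges the two and collides with the hospitalisation criterion. Two sites could follow the same protocol and classify the same admission differently.

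The classification decides the route. SAEs are the only events that the protocol routinely sends to the Independent Monitoring Committee. If a surgical admission is an AE, it is recorded on the CRF for routine return and captured as a secondary outcome at six months, and no sentence carries it to the committee.

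The additional symptom criterion raises a separate question. Its clock starts at a physiotherapy or exercise session, and the arms differ greatly in how many sessions they have. The same symptom, at the same background rate, would then be counted as an SAE far more often in one arm than in the other. The definitions may also outlive the pilot, since section 2.7.2.1 foresees that pilot data could contribute to a definitive trial.

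**Working it through.** The protocol gives no figure to reproduce on this point. The first part is a comparison of texts, the second is arithmetic on the time window.

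**1. Surgery: the rules side by side**

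| Rule | Result for a surgical admission for progression |
|---|---|
| 4.1.2, hospitalisation criterion | SAE (admission is implied by the description in 1.1, although the protocol does not say so outright) |
| 4.2, list of expected events | AE, not reported to the ethics committee |
| 4.2, events fitting the serious criteria | SAE form within 24 hours, no exception stated |
| 4.2, all SAEs | Reported to the Independent Monitoring Committee |
| 4.2, ethics committee rule | Not reported, because expected |

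The last row shows that listing surgery as an AE is not needed for its apparent purpose: an expected SAE is already exempt from ethics committee reporting. The other two listed events, bracing and mild soreness, meet no general criterion as described, so there is no conflict for them.

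How many such events there might be within six months is not stated. Under assumed six-month rates *p*, expected events among 50 participants are 50*p*, and the chance of at least one is 1 - (1 - *p*)^50:

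- *p* = 1%: 0.5 events, chance 0.39
- *p* = 5%: 2.5 events, chance 0.92

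**2. The 48-hour window**

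Inputs: six months = 365.25/2 = 182.6 days; control 1-2 sessions (section 2.6.1.3); exercise arm 6-9 supervised sessions (Table 1) plus daily home exercise (section 2.6.1.2); 25 per arm (Figure 2).

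Share of follow-up inside the window = min(1, 2 days × sessions / 182.6):

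- Control: 2/182.6 = 1.1% to 4/182.6 = 2.2%
- Exercise arm, supervised sessions only: 12/182.6 = 6.6% to 18/182.6 = 9.9%

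With home exercise on *k* evenly spread days a week, the share is min(1, 2*k*/7):

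- *k* = 1: 29%
- *k* = 2: 57%
- *k* = 3: 86%
- *k* = 4 or more, including daily as planned: 100%

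Now assume that a proportion *q* of each arm has one qualifying symptom episode at a random time, with no treatment effect. Expected SAEs under this criterion are 25 × *q* × share:

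| *q* (assumed) | Exercise, full coverage | Control, 1-2 sessions |
|---|---|---|
| 5% | 25 × 0.05 = 1.25 | 0.01 to 0.03 |
| 20% | 25 × 0.20 = 5.0 | 0.05 to 0.11 |

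So with identical background rates the criterion yields about 1.25-5.0 events in the exercise arm against 0.01-0.11 in control. With supervised sessions only, the exercise figure falls to 0.08 (5%, 6 sessions) to 0.49 (20%, 9 sessions).

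**The case against.** The best defence on surgery is that section 4.2 names only the ethics committee as not receiving the event. Its sentence on events fitting the serious criteria follows the list and carries no exception, so one fair reading sends a surgical admission to the monitoring committee after all. The listed event is also that surgery is needed, and a decision to operate is not itself an admission. Section 7.7 says the committee reviews SAEs primarily, not exclusively, and section 7.6 lets the management group refer significant issues to it. Nor is surgery lost: it is a secondary outcome in both arms, and every adverse event goes on the CRF. All of this stands. It means that the text is ambiguous, and that non-receipt by the committee is not a stated rule. It does not resolve which instruction prevails.

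On the symptom criterion, a trigger tied to sessions is a defensible way to pick up harm from the intervention, and causality is assessed for each SAE. Section 6.1 does not list a between-arm comparison of SAEs. The large contrast above assumes near-daily exercise, which the protocol treats as uncertain. And exercise session is not defined, so a control participant's own exercise might count. These limit the point to how the counts may be read.

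Three stronger readings are tempting and are not supported:

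- **That the committee is not told of surgery.** This is an inference from the AE label; the text excludes the ethics committee only.
- **That pain is serious only near a session.** The criterion is introduced as an addition. Symptoms that meet a general criterion are SAEs in either arm at any time.
- **That about 5 of 25 controls would have surgery recorded only as an AE.** This applies the 20% from section 2.7.1, which is a planning assumption for the definitive trial with no time horizon. The pilot follows participants for six months and excludes those on a waiting list for surgery in that period, so 20% is at most an upper bound here.

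**Conclusion.** The conflict over surgery holds. A surgical admission meets a general SAE criterion and is also assigned to the AE list, with no rule of precedence. If sites follow the list, the only independent safety body has no routine written route to these events. The number affected in six months is unknown; at an assumed 1-5% it would be 0.5-2.5 among 50.

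The unequal window holds as a secondary point. Coverage is about 1-2% of follow-up in control and up to 100% in the exercise arm, or 86% at three home sessions a week. It concerns only symptoms that limit activity for more than 3 days and meet no general criterion. The event counts rest on an assumed background rate of 5-20%, equal in both arms and random in time. The conclusion is that counts under this criterion should not be read as a comparison between arms, not that the criterion is wrong as a trigger for possible intervention harm.

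**What to change.** **Surgery.** Reconcile sections 4.1.2 and 4.2 by stating that surgery for progression that involves admission remains serious but expected. It needs no report to the ethics committee, which the unexpected-and-related rule already ensures. State in section 4.2 or 7.7 that these events are included, by arm, in what the Independent Monitoring Committee receives.

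**Activity-limiting symptoms.** Record onset or increase of symptoms that restrict activities for more than 3 days alike in both arms, for example as AEs, with time since the last session noted for the causality assessment. The session-linked SAE trigger can then stay. Dropping the 48-hour condition outright is a trade-off rather than a clear gain, because many background pain flares would become SAEs. Define exercise session, including whether a control participant's own exercise counts. If the trigger stays, add a sentence that counts under it are not for comparison between arms.

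The cost is protocol and form wording and a little more recording at sites.
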